ANNEX 2. ENCEPP CHECKLIST FOR STUDY PROTOCOLS

Not applicable

2. LIST OF ABBREVIATIONS

Term	Definition / description
ADR	Adverse Drug Reaction
AE	Adverse event
ATT	Average treatment effect in the treated
BI	Boehringer Ingelheim Pharma GmbH & Co. KG
CAT™	COPD Assessment Test
CDF	Cumulative distribution function
CI	Confidence Interval
COPD	Chronic obstructive pulmonary disease
CTP	Clinical trial protocol
FEV1	Forced expiratory volume in one second
GERD	Gastroesophageal reflux
GP	General Practitioner
GOLD	Global Initiative for Chronic Obstructive Lung Disease
ICH	International Conference on Harmonisation
ICS	Inhaled corticosteroids
IPTW	Inverse probability of treatment weighting
IRB	Institutional Review Board
LABA	Long-acting beta2-adrenoceptor agonist
LAMA	Long-acting anticholinergic bronchodilator
Max	Maximum
MedDRA	Medical Dictionary for Drug Regulatory Activities
Min	Minimum
mMRC	Modified Medical Research Council Scale
MS	Matched set
NCI	National Cancer Institute
NIS	Non-interventional study
PGE	Physician's global Evaluation
PP	Per-protocol set
PS	Propensity score
PV	Protocol violation

Proprietary confidential information © 2020 Boehringer Ingelheim International GmbH or one or more of its affiliated companies

Term	Definition / description
SAS	Statistical analysis software
SmPC	Summary of Product Characteristics
TEAE	Treatment-emergent AE
TS	Treated set
TSAP	Trial Statistical Analysis Plan

3. INTRODUCTION

As per ICH E9^[1], the purpose of this document is to provide a more technical and detailed elaboration of the principal features of the analysis described in the protocol, and to include detailed procedures for executing the statistical analysis of the primary and secondary variables and other data.

This TSAP assumes familiarity with the Clinical Trial Protocol (CTP), including Protocol Amendments. In particular, the TSAP is based on the planned analysis specification as written in CTP Section 9.7 “Data Analysis”. Therefore, TSAP readers may consult the CTP for more background information on the study, e.g., on study objectives, study design and population, treatments, definition of measurements and variables, planning of sample size, randomization.

SAS® Version 9.4 or higher will be used for all analyses.

4. CHANGES IN THE PLANNED ANALYSIS OF THE STUDY

None.

5. ENDPOINT(S)

5.1 PRIMARY ENDPOINT(S)

Primary outcomes are:

- Difference between mMRC score at baseline (visit 1) and mMRC score after end of observation (ca. 12 weeks of treatment, Visit 2)
- Difference between CATTM score at baseline (visit 1) and CATTM score after end after end of observation (ca. 12 weeks of treatment, Visit 2)
- For descriptive analysis the CATTM will additionaly be stratified in low (0-10 points), medium (11-20 points), high (21-30 points) and very high (31-40 points)

The primary outcomes are reported in a descriptive manner, will be compared in an explorative manner and are not safety outcomes.

5.2 SECONDARY ENDPOINT(S)

Secondary endpoints to be determined and compared in an exploratory manner include:

[figure not shown]
- Patients' general condition according to the Physician's Global Evaluation (PGE) score at baseline and end of the observation period
- Patient satisfaction with inhaler and therapy at end of observation period according to a seven-point ordinal scale (ranging from very dissatisfied to very satisfied as documented in non-interventional BI studies (BI 1237-0042, 1237-0043, 1237-0044, 1237-0045, 1237-0065, 1237-0072)
- Proportion of responders with $\Delta_{\text{mMRC}} \geq 1$ and the proportion of responders with $\Delta_{\text{CAT}} \geq 2$

The secondary outcomes are not safety outcomes.

Comparative analyses on secondary endpoints will be performed as for the main analysis but only using the primary analytical approach (propensity score matching).

Proprietary confidential information © 2020 Boehringer Ingelheim International GmbH or one or more of its affiliated companies

6. GENERAL ANALYSIS DEFINITIONS

6.1 TREATMENT(S)

In the presented study, treatment with Spiolto® Respimat® will be according to product information. Patients will be treated with Spiolto® Respimat® or triple therapy and be observed for approximately 12 weeks.

Other LAMA, LABA and/or ICS therapy will be performed according to label as described in the respective SmPCs.

6.2 IMPORTANT PROTOCOL DEVIATIONS

Table 6.2: 1 defines the different categories of important protocol violations (PVs). The final column describes which PVs will be used to exclude subjects from the different patient analysis sets^[2].

Table 6.2: 1 Important protocol violations

Category/Code		Description	Requirements	Excluded from
A		Entrance criteria not met		
	A1.1	Inclusion criterion 1 (Diagnosis of COPD)	Not met as specified in the protocol	PP, MS
	A1.2	Inclusion criterion 2 (Symptomatic (with regard to dyspnea (mMRC Dyspnea score ≥ 1) AND with regard to symptoms (CAT Score ≥ 10) at the same time))	Not met as specified in the protocol	PP, MS
	A1.3	Inclusion criterion 3 (Patients on LABA/ICS maintenance therapy who are switched to Spiolto® Respimat® in the new reusable inhaler or a free/fixed triple combination of LABA + LAMA + ICS at Visit 1 at the discretion of the treating physician.)	Not met as specified in the protocol	PP, MS
	A1.4	Inclusion criterion 4 (Adults who are contractually capable and mentally able to understand and follow the instructions of the study personnel)	Not met as specified in the protocol	PP, MS
	A1.5	Inclusion criterion 5 (Male or female aged ≥ 40 years of age)	Not met as specified in the protocol	PP, MS
	A1.6	Inclusion criterion 6 (Written informed consent prior to study participation)	Not met as specified in the protocol	PP, MS
	A1.7	Inclusion criterion 7 (The patient is willing and able to follow the procedures outlined in the protocol)	Not met as specified in the protocol	PP, MS
	A2.1	Exclusion criterion 1 (Patients with contraindications acc. to SmPC)	Met as specified in the protocol	PP, MS
	A2.2	Exclusion criterion 2 (Patients not on LABA/ICS maintenance treatment at visit 1, e.g., mono or dual bronchodilation only, ICS only, or a triple combination of LAMA + LABA + ICS (either as a	Met as specified in the protocol	PP, MS

Category/Code	Description	Requirements	Excluded from
	fixed combination product or as separate components))		
A2.3	Exclusion criterion 4 (Pregnant and/or lactating females)	Met as specified in the protocol	PP, MS
A2.4	Exclusion criterion 5 (Acute exacerbation of COPD (within 4 weeks prior to Visit 1))	Met as specified in the protocol	PP, MS
A2.5	Exclusion criterion 6 (Frequently exacerbating COPD patients, i. e. patients with ≥ 2 moderate exacerbations within the last 12 months or ≥ 1 exacerbation leading to hospitalization within the last 12 months ¹)	Met as specified in the protocol	PP, MS
A2.6	Exclusion criterion 7 (Acute respiratory failure (pH <7,35 and/ or respiratory rate >30/min within 3 months prior to Visit 1))	Met as specified in the protocol	PP, MS
A2.7	Exclusion criterion 8 (History or current diagnosis of asthma)	Met as specified in the protocol	PP, MS
A2.8	Exclusion criterion 9 (History or current diagnosis of asthma-COPD overlap)	Met as specified in the protocol	PP, MS
A2.9	Exclusion criterion 10 (History or current diagnosis of allergic rhinitis within the last 5 years)	Met as specified in the protocol	PP, MS
A2.10	Exclusion criterion 11 (History or current diagnosis of lung cancer within the last 5 years)	Met as specified in the protocol	PP, MS
A2.11	Exclusion criterion 12 (Participation in a parallel interventional clinical trial)	Met as specified in the protocol	PP, MS
B	Informed consent		
B1	Informed consent not available/not done (Inclusion criterion 1/Exclusion criterion 3)	IC 01 not met as specified in the protocol or informed consent date missing	All

¹ Definitions of exacerbation severity according to German Pulmonary Society Guideline (DGP-Leitlinie 2019).

6.3 PATIENT SETS ANALYZED

Treated set (TS): All patients with informed consent who have received at least one dose of Spiolto® Respimat® or triple combination (free or fixed LAMA + LABA+ ICS).

[figure not shown]
Per-protocol set (PP): All patients with informed consent who met all inclusion criteria as well as no exclusion criteria and have received at least one dose of Spiolto® Respimat® or triple combination (free or fixed LAMA + LABA+ ICS).

Matched set (MS): Subset of PP excluding all patients who could not be matched in the propensity score matching.

Table 6.3: 1 Patient sets analyzed

Class of endpoint	Patient set		
	TS	PP	MS
Primary	X	X	X
Secondary endpoints	X		X
Safety endpoints	X		
Demographic/baseline	X		X

If the number of patients excluded from the PP is small (<10% of the TS), then analyses on this set may not be conducted.

6.5 POOLING OF CENTRES

This section is not applicable because centre/country is not included in the statistical model.

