9.2 SETTING

9.2.1 Study sites

Data collection of approximately 900 patients from approximately 150 recruiting sites in Germany is planned. Site selection will be performed to reflect routine COPD care in Germany in order to secure representativeness of the COPD population.

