9.2.3 Study visits

Patients will be enrolled consecutively and will be followed over an observational period of approximately 12 weeks. Two study visits will be performed.

Patients will be attributed to either group (triple therapy or Spiolto® Respimat®) on the investigator's discretion and patient's consent before study start at visit 1 (Baseline).

If possible and manageable and in compliance with the investigator's decision, a 1:1 group distribution of the patients included per site should be aimed at. However, a strict distribution scheme is not given.

At Visit 1 (baseline), after information and signature of the Informed Consent Form, the patient will be included into the NIS. The patient will of course have enough time for considering study participation.

At Visit 2, after approximately 12 weeks of treatment, the observation of the patient will end. The respective exams and data to be collected are listed in [Table 9.2.3.1](#).

Table 9.2.3.1: Visit flow chart and data collection parameters

| Parameter | Visit 1; baseline visit | Visit 2; approx. 12 weeks after baseline visit |
|--|-------------------------------|---|
| Informed Consent | X | |
| Specialization of attending physician (GP, pulmonologist, internal specialist) | X | |
| Inclusion / Exclusion Criteria | X | |
| Patient demographics (age, gender, height, and weight) | X | |
| History of COPD | X | |
| Rationale for changing COPD maintenance therapy | X | |
| Number and severity of exacerbations in the last 12 months | X | |
| Number of exacerbations leading to hospitalization in the last 12 months | X | |
| Device training (yes/no), reason for no training | X | |

Table 9.2.3.1 (cont'd): Visit flow chart and data collection parameters

| Parameter | Visit 1; baseline visit | Visit 2; approx. 12 weeks after baseline visit |
|--|-------------------------------|---|
| COPD severity based on GOLD assessment ^{iv} (GOLD patient groups) | X | |
| GOLD spirometric classification, if available ^v , incl. date of examination | X | |
| Eosinophils in peripheral blood, if available | X | |
| Smoking history, current status, pack-years | X | |
| Concomitant diseases / Comorbidities | X | X |
| Current COPD related and other relevant concomitant medication | X | X |
| mMRC breathlessness scale, completed by the patient | X | X |
| Health and functional status by CAT TM questionnaire, completed by patient | X | X |

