Because mMRC and CAT™ are both of interest as primary endpoints here, the required sample size for the NIS equals the higher of the two respective estimates, i.e. 864 patients in total (432 patients per group).

Patients will be attributed to either group (triple therapy or Spiolto® Respimat®) on the investigator's discretion and patient's consent at visit 1. If possible and manageable and in compliance with the investigator's decision, a 1:1 group distribution of the patients included per site should be aimed at. However, a strict distribution scheme is not given.

Measures to be considered in case of substantially unequal recruitment include the early closing one of the treatment arms earlier (i.e., when its target size is reached) and the analysis of unequal group sizes (1:2, 1:3 or 1:4).

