9.9 LIMITATIONS OF THE RESEARCH METHODS

This prospective NIS aims to investigate the comparative effectiveness of Spiolto® Respimat® in the new reusable inhaler vs any free or fixed-dosed triple therapy (LAMA + LABA + ICS) in reducing dyspnoea (as measured via mMRC questionnaire) and symptom burden (as measured via CAT™) in COPD patients who are dyspnoeic despite LABA/ICS maintenance treatment when switched to either Spiolto® Respimat® or to any triple therapy, both in a real-word setting.

A NIS appears the most suitable instrument for obtaining information about the use of medicines in everyday therapeutic practice and thus for investigating prospectively questions in everyday therapeutic practice.

Consecutive enrolment will be employed to minimize selection bias. The entry criteria are non-restrictive which will permit the enrolment of a broad patient population. The choice of treatment is at the discretion of the investigator.

Selection bias could occur at the site level and the patient level. To minimize the site level selection bias, the goal is to have participating centers with access to all available and approved treatment options in that country for the targeted COPD patients. To minimize selection bias at the patient level, consecutive enrolment is performed. Information bias will be minimized by the use of standard eCRF, questionnaire and physicians' training on the study protocol.

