7.3 PRIMARY ENDPOINTS

The primary outcomes are reported in a descriptive manner, will be compared in an explorative manner and are not safety outcomes. For the three primary outcomes the comparative treatment effect will be estimated along with 95% confidence intervals (CI).

For absolute changes in total mMRC and CATTM score between baseline and end of observation, summary statistics will be provided. Furthermore linear regression will be used to analyse the change in mMRC and CATTM score. The model will adjust for clustering (matched patients) using generalized estimating equations (GEEs) and take the respective baseline variable as covariate into account.

In an additional analysis it will be investigated if the therapy effect is heterogeneous with respect to the GOLD spirometric classification and the GOLD patient group, respectively. The stratified estimators with their corresponding 95% confidence interval will be shown. If

appropriate, a p-value of the interaction of treatment and GOLD may be provided. If some of the strata are too small they will be omitted from the analysis. **mMRC and CAT™ score**

The mMRC Dyspnea Scale consists only of one question on symptom severity and yields a score of either 0, 1, 2, 3 or 4.

The total CAT™ score ranges from 0 to 40. A higher score is indicative of worse status. According to the manual missing values will not be imputed, no total score will be calculated if at least one item is missing. However a single imputation will be done as sensitivity analysis, by imputing the response for the missing question as mean of the other questions of the respective patient.

The total CAT™ score and the corresponding subscales are calculated as follows, in case that answers to all 8 items are available:

$$\text{Total CAT}^{\text{TM}} \text{ score} = \sum_{i=1}^8 \text{item}_i$$

The estimation of the treatment effect is subject to potential confounding. Therefore, beside the analysis based on data as collected adjusted analyses are required. Multiple analytical approaches will be applied to allow an assessment of the sensitivity of the results to these approaches:

- Propensity score matching (primary analysis; requires data to be discarded from the analysis)
- Propensity score weighting (uses the complete data set)
- Multivariable regression modeling (uses the complete data set)

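### Site is left out of every model and every standard error; if outcomes correlate within site, the 95% intervals are somewhat too narrow or slightly too wide, depending on each site's treatment mix

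*SAP*

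**What the plan says.** SAP 6.5 on pooling of centres reads, in full: "This section is not applicable because centre/country is not included in the statistical model". SAP 7.3 gives the only clustering that the plan models: "The model will adjust for clustering (matched patients) using generalized estimating equations (GEEs) and take the respective baseline variable as covariate into account". Matching is on the logit of the propensity score alone, so the two members of a pair can come from different sites. The covariate lists for the propensity score and for the regression model are the same. Their only provider-level variable is physician specialty, in three classes. The SAP describes no site-level variance for the weighted or regression analyses, and no sensitivity analysis by site.

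On the design side, Protocol 9.2.1 states: "Data collection of approximately 900 patients from approximately 150 recruiting sites in Germany is planned". Protocol 9.9 states: "The choice of treatment is at the discretion of the investigator". Protocol 9.2.3 says of the treatment mix that "a 1:1 group distribution of the patients included per site should be aimed at. However, a strict distribution scheme is not given". If recruitment becomes unequal, Protocol 9.5.1 contemplates closing one arm early and analysing ratios up to 1:4.

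**The concern.** Patients at one site share a practice, a catchment area and whoever chooses their treatment there, so their outcomes may be correlated. Whether this matters for a treatment comparison depends on how treatment is spread within sites.

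- If sites lean to one treatment, part of the between-site variation enters the treatment contrast, and a standard error that ignores site is too small.
- If every site is split 1:1, the site effect largely cancels within site, and that standard error is too large.
- If treatment is unrelated to site, it is about right.

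The plan leaves the mix open. The 1:1 aim is not binding, and closing one arm early would send later patients at every site to the other arm. The primary results are effect estimates with 95% confidence intervals and tests of the coefficients (Protocol 9.7.1), so calibration matters even in an exploratory study. The three analytical approaches are meant to show how sensitive the results are to method. All three share this omission, so agreement among them could not reveal it.

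**Working it through.** **Inputs from the documents.** CAT margin 2 points, SD 7, one-sided alpha 2.5%, power 90%, 518 evaluable patients (259 per group), 40% total loss of which 10% is ordinary dropout (Protocol 9.5.1); about 900 patients and 150 sites (Protocol 9.2.1).

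**Assumed, because the documents give neither.** ICC of 0.01 to 0.20, and the within-site correlation of treatment, r.

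**Step 1: reproduce the planned size.** The normal formula is n = 2 × SD² × (z₀.₉₇₅ + z₀.₉₀)² / margin² = 2 × 49 × (1.9600 + 1.2816)² / 4 = 257.4, so 258 per group. The exact t-test gives 259, as stated, hence 518. Then 518/0.6 = 863.3, so 864, as stated. Both figures assume independent patients; there is no design effect.

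**Step 2: patients per site.** Matched set: 518/150 = 3.45. Weighting and regression, after 10% dropout only: 900 × 0.9/150 = 5.40.

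**Step 3: formulas.**
- Variance ratio (true over site-ignoring): V = 1 + (m − 1) × ICC × r, with m patients per site. One treatment per site gives r = 1. Treatment unrelated to site gives r = 0 and V = 1. Exact 1:1 in every site gives r = −1/(m − 1), so V = 1 − ICC.
- Coverage of the site-ignoring 95% interval: 2Φ(1.96/√V) − 1.
- CAT power at 518 when the variance is computed correctly: Φ(2/(0.615√V) − 1.96), where 0.615 = 7√(2/259).

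**Worked case** (matched set, ICC 0.05, one treatment per site): V = 1 + 2.45 × 0.05 = 1.123 and √V = 1.060. Coverage is 2Φ(1.96/1.060) − 1 = 93.6%. Power is Φ(3.251/1.060 − 1.96) = 86.6%.

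**Results** (SE ratio is √V):

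| ICC | Matched, one treatment per site: SE ratio / coverage / CAT power | Exact 1:1 in every site: SE ratio / coverage | Unmatched, one treatment per site: SE ratio / coverage |
|---|---|---|---|
| 0.01 | 1.012 / 94.7% / 89% | 0.995 / 95.1% | 1.022 / 94.5% |
| 0.05 | 1.060 / 93.6% / 87% | 0.975 / 95.6% | 1.105 / 92.4% |
| 0.10 | 1.116 / 92.1% / 83% | 0.949 / 96.1% | 1.200 / 89.8% |
| 0.20 | 1.221 / 89.2% / 76% | 0.894 / 97.2% | 1.371 / 84.7% |

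A partial site preference (r = 0.3) in the matched set gives 94.6% at ICC 0.05 and 94.1% at 0.10.

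**In CAT points.** The planned half-width is 1.96 × 0.615 = 1.21. With one treatment per site it should be 1.21 × 1.060 = 1.28 at ICC 0.05 and 1.21 × 1.116 = 1.35 at ICC 0.10.

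**Step 4: check by simulation.** With matching blind to site and a pair-level standard error, one treatment per site gave coverage of 92.9% at ICC 0.05 and 91.2% at 0.10; balanced sites gave 95.4% and 95.2%. With ICC zero the same simulation gave 94.6% to 95.7%, so differences of about one point are within its noise. A further simulation with graded site preference gave pair-only coverage of about 94–96% at ICC 0.05, 93–95% at 0.10 and 91–94% at 0.20, and about 96% with forced 1:1. Clustering on pair and site gave about 94–96% in every setting.

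**The case against.** The best case for leaving the plan alone has five parts. The study is declared exploratory. No ICC is known. Sites are small. The per-site 1:1 aim works against the worst case. Physician specialty is already adjusted for. At ICC 0.05 or below, the primary interval is barely affected.

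Most of this stands as a limit on size. It does not answer the omission. Three specialty classes cannot stand in for about 150 sites, the 1:1 aim is not enforced, and confidence intervals and tests are planned whatever the study is called.

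A reader might infer more than the documents support:

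- **That the intervals are wrong, or do not cover 95%.** This needs a non-zero ICC and a treatment mix related to site, or balanced within it. The documents establish neither, and with treatment unrelated to site the SE ratio is 1.
- **That the design effect is 1.25, coverage 92.0% and CAT power 83% at ICC 0.05.** This comes from 900/150 = 6 patients per site, which counts enrolled patients. The primary analysis is planned on 518, or 3.45 per site, which gives 1.12, 93.6% and 86.6%.
- **That physicians assess the primary outcomes.** Patients complete both the mMRC and the CAT. Only the Physician's Global Evaluation, a secondary endpoint, is rated by the physician. Nor do the documents say who gives device training.
- **That the interval will formally be judged against 2 points.** The margin appears only in the sample size section; the SAP has no non-inferiority decision rule.

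**Conclusion.** The point holds in conditional form and is modest in size for the primary analysis. The omission is explicit and runs through all three approaches. The direction of any error depends on the treatment mix within sites, which the plan neither controls nor models.

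At ICC up to 0.10, matched-set coverage runs from 92.1% (one treatment at every site) to 96.1% (exact 1:1 at every site). Weighting and regression are more exposed on the narrow side, because more patients per site remain. Only the corner of ICC 0.20 with one treatment per site takes the matched analysis below 90%.

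These figures rest on an assumed ICC and on equal site sizes with 518 patients spread over all 150 sites, and they ignore the effect of unequal weights. Site sizes will vary: with 15 analysed patients per site, ICC 0.05 and one treatment per site, V = 1 + 14 × 0.05 = 1.70, the SE ratio is 1.30 and coverage is 86.7%. This is a worthwhile correction, not a flaw that invalidates the study.

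**What to change.** Replace SAP 6.5 and extend SAP 7.3 so that standard errors in all three approaches account for site:

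- **Matched analysis:** cluster-robust variance on both pair and site, computed as the pair-clustered plus the site-clustered minus the pair-by-site-clustered variance matrix. Use an independence working correlation in all three fits, so that the coefficients are identical. If matching goes beyond 1:1, the matched set takes the place of the pair.
- **Weighting and regression:** sandwich variance clustered on site.
- **Reporting:** number of patients and treatment mix by site, so that readers can see which way any error would have run.

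The fixed part of the models stays as it is. Site identity is already available (SAP 6.6 has removals documented by site), so no new data are needed. The cost is a paragraph of SAP text and a few lines of code. The downside is a slightly wider interval if sites favour one treatment. The change corrects the variance only: if sites differ in both prognosis and treatment preference, site-level confounding of the point estimate remains, and the report should say so.
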